## **10.7 Primary Safety Analysis**

The primary safety variable is the evaluation of adverse events up to the 3-month visit after treatment. Adverse events reported at each scheduled study visit. Adverse event rates (total and categorized by duration) will be summarized as counts and percentages. Stratification on type, onset after treatment, duration (0-7 days, 8-14 days, 15-28 days, and more than 28 days), severity, and relationship to study device and/or procedure will also be provided. Adverse events self-reported in the Subject Diary will be summarized in patient listings.

## **10.8 Secondary Safety Analysis**

The secondary safety variable is the evaluation of the pain and discomfort after treatment as reported by the subject on a 10-point visual analog scale (VAS). Results of the VAS on a scale of 0 to 10 will be summarized descriptively utilizing mean, standard deviation, minimum, maximum, median, and the 95% confidence interval of the mean and mean change from baseline.

## **10.9 Additional Analyses**

Other endpoints to be evaluated include:

**10.9.1** FWS  $\geq 1$ -score improvement and  $\geq 75\%$  agreement with at least an “improved” rating by the subject on the modified GAIS. An “improvement” on the modified GAIS by the subject at the 3-month visit will be classified as “improved,” “much improved,” or “very much improved.” All other ratings on the modified GAIS will be classified as “no improvement.” Cross-tabulation of improvement status of modified GAIS versus 1-score FWS response will then be summarized as counts and percentages.

**10.9.1.1** Magnitude of improvement measured by the mean change in FWS from baseline to 3-month visit. Descriptive summary statistics (number of observations, mean, standard deviation, minimum, maximum, median, 95% confidence interval of the mean) will be used for summarizing the change in FWS from baseline to the 3-month visit. The FWS from baseline to the 3-month visit will also be stratified on both the treating-investigator and subject modified GAIS.

**10.9.1.2** Subject satisfaction with procedure recorded at the 3-month visit. Results of VAS on a scale of 0 to 10 will be summarized descriptively utilizing mean, standard deviation, minimum, maximum, median, and the 95% confidence interval of the mean. Cross tabulation of subject satisfaction/improvement versus 1-score FWS response will be summarized as counts and percentages.

**10.9.1.3** Achievement of re-epithelialization by facial zone (and across facial zones) at the 10-day, 1-month and 3-month follow-up visits as reported by the study investigator and/or Independent

Photographic Reviewers (as applicable). Descriptive summary statistics (number of observations, mean, standard deviation, minimum, maximum, median, 95% confidence interval of the mean) will be used for summarizing the achievement of re-epithelialization by facial zone and across facial zones at all follow-up visits through the 3-month visit.

**10.9.1.4** Mean duration (days) until subject feels comfortable going in public after treatment as reported the study subject. Descriptive summary statistics (number of observations, mean, standard deviation, minimum, maximum, median, 95% confidence interval of the mean) will be used for summarizing the mean duration for study subject to feel comfortable after treatment.

**10.9.1.5** Daily 10-point Visual Analog Scale (VAS) pain assessments following treatment through the 10 day follow-up visit by diary day with a change from the VAS pain score at baseline.

Descriptive summary statistics by diary day (number of observations, mean, standard deviation, minimum, maximum, median, 95% confidence interval of the mean) and the change from the VAS pain score at baseline will be provided.

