### 9.2 Missing Data

If applicable, a list of subjects who were withdrawn/lost to follow-up from the study and associated reasons will be provided.

Subjects with missing 3-month FWS data will be imputed as having no change from baseline. No other imputations for missing data will be employed. Furthermore, no estimation of missing data for self-reported pain within the 10 day Subject Diary will be imputed.

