#### 10.2.2 Full Analysis Set (FAS)

All subjects enrolled in the study who have a FWS value at baseline will be included in the FAS. Subjects with missing FWS data at the 3-month visit will be imputed as no change and included in the FAS population. Efficacy outcomes will be evaluated in the FAS.

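### The no-change rule for missing 3-month FWS also feeds the descriptive mean change, so its n, SD and 95% CI include zeros that nobody observed

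*SAP*

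**What the plan says.** SAP 9.2 states the rule for the FWS data as such, not for one endpoint: "Subjects with missing 3-month FWS data will be imputed as having no change from baseline". It then closes the list: "No other imputations for missing data will be employed".

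SAP 10.2.2 repeats the rule and keeps the subjects in: "Subjects with missing FWS data at the 3-month visit will be imputed as no change and included in the FAS population". It assigns the population without exception: "Efficacy outcomes will be evaluated in the FAS". Membership needs only enrolment and a baseline score: "All subjects enrolled in the study who have a FWS value at baseline will be included in the FAS".

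SAP 10.9.1.1 defines the endpoint as "Magnitude of improvement measured by the mean change in FWS from baseline to 3-month visit" and lists what will be reported: "number of observations, mean, standard deviation, minimum, maximum, median, 95% confidence interval of the mean) will be used for summarizing the change in FWS". It names no other population and no observed-case version. The same paragraph adds a breakdown: "The FWS from baseline to the 3-month visit will also be stratified on both the treating-investigator and subject modified GAIS".

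**The concern.** For a yes/no responder endpoint, counting a missing subject as a failure is a defensible conservative choice. A mean is different. Entering zero asserts that the subject was exactly at baseline at 3 months. The rule does so even where that subject's FWS at another visit shows improvement, and SAP Table 1 schedules FWS at 10 days, 1 month and 6 months as well.

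The figure meant to show how much wrinkles improve then also depends on how many 3-month scores are missing. The count of observations includes values that were never observed, and the interval treats them as data.

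There is a smaller, related point about the GAIS breakdown. The modified GAIS is not imputed, so a subject with no 3-month GAIS stays in the overall mean but falls into no GAIS stratum. The denominators may then differ within one paragraph of results.

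**Working it through.** **Inputs.** SAP 8.4 gives 50 evaluable subjects, up to 10% attrition and 55 enrolled. It gives no mean or SD for FWS change, so those values are assumptions and are varied below.

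**The plan's own figures first.** With N = 50, P0 = 0.75 and one-sided alpha 0.05, the smallest rejecting count is 43 of 50 (exact alpha 0.0453). Power at P = 0.90 is 0.878, which agrees with the stated 88% or so. The planned loss is 55 − 50 = 5 subjects, and 5/55 = 9.1%, within the stated ceiling.

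**Shift in the mean.** With k of N changes set to zero and observed mean m, the reported mean is m × (N − k)/N. With N = 55:
- k = 3: 52/55 = 0.945, a shift of −5.5%
- k = 5: 50/55 = 0.909, a shift of −9.1%

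The percentage does not depend on m.

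**Effect on the interval.** Let m′ be the reported mean and s the observed SD. The imputed variance is [(N − k − 1)s² + (N − k)m² − N·m′²]/(N − 1). For m = 2.0, s = 1.0 and k = 5 this is (49 + 200 − 181.8)/54 = 1.244, so the SD is 1.115. Results with 5 missing:

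| Assumed mean, SD | Observed cases (n = 50) | Zeros included (n = 55) |
|---|---|---|
| 1.0, 1.0 | 1.00 (0.72 to 1.28) | 0.91 (0.64 to 1.18) |
| 1.5, 1.0 | 1.50 (1.22 to 1.78) | 1.36 (1.08 to 1.65) |
| 2.0, 1.0 | 2.00 (1.72 to 2.28) | 1.82 (1.52 to 2.12) |
| 3.0, 1.0 | 3.00 (2.72 to 3.28) | 2.73 (2.38 to 3.08) |

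**Coverage if loss is unrelated to outcome.** This was simulated with normal changes and t-based 95% intervals, at least 40,000 trials per setting.
- Mean 2.0, SD 1.0: about 95% with 1 missing, 93% with 2, 91% with 3 and 81% with 5.
- Mean 2.0, SD 1.5: about 88% with 5 missing.
- Mean 1.0, SD 1.0: about 94% or better with up to 3 missing, and about 91% with 5.
- Observed cases only: about 95% throughout.

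**Coverage if loss is related to outcome.** Here mean is 2.0, SD 1.0 and 5 are missing, and the target is the mean over all 55 subjects.

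| Missing subjects' true mean change | Target | Zeros included | Observed only |
|---|---|---|---|
| 2.0 (same as the rest) | 2.00 | 81% | 95% |
| 1.0 (half as much) | (50×2 + 5×1)/55 = 1.91 | 94% | 90% |
| 0 (none) | (50×2 + 5×0)/55 = 1.82 | 98% | 76% |

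**The case against.** The strongest reply is that this is a prespecified choice, stated twice, which works against the device. It affects a descriptive row to which no test or success criterion is attached. That is correct, and it limits the severity. It does not remove the point, because the row is offered as the size of the effect, and following the plan to the letter mixes that size with missingness.

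A reader might infer that the interval simply fails to give 95% coverage. The documents do not support that flat statement. The shortfall depends on loss being unrelated to outcome, on an assumed mean and SD, and on attrition near its ceiling. The second coverage table shows that observed cases can do worse than the plan's rule if missing subjects improved less.

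Nor is the interval always too narrow. With 5 missing, the half-width falls from 0.426 to 0.394 at mean 1.0 and SD 1.5, but rises from 0.227 to 0.313 at mean 3.0 and SD 0.8. What is constant is the shift towards zero and the treatment of imputed values as data.

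A reader might also infer that the overall and GAIS-stratified results cannot be reconciled. That goes too far. FWS and GAIS are separate assessments with partly different raters (SAP Table 1, notes 4 and 8), so a missing FWS need not mean a missing GAIS. Differing denominators are common when the stratifying variable is incomplete, and they can be shown.

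Finally, 10.9 mixes efficacy, healing and pain items and names no population, so the reach of 10.2.2 is partly inferred. The general wording of 9.2 is enough to carry the reading.

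**Conclusion.** The point stands at low severity. Read together, 9.2, 10.2.2 and 10.9.1.1 put unobserved zeros into the n, mean, SD and 95% CI of the 3-month FWS change.

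The reduction against the observed-case mean is arithmetic and certain: 9.1% at the planned maximum loss, and less with fewer missing. It is bias only to the extent that missing subjects did improve. The 81% coverage figure is the low end of the settings examined and rests on the assumed mean and SD and on loss unrelated to outcome; with 1 or 2 missing the effect is small.

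Nothing here touches the primary responder analysis.

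**What to change.** - **9.2 (and the matching sentence in 10.2.2):** limit the no-change rule to the endpoints based on an FWS improvement of at least one score.
- **10.9.1.1:** report the mean change and 95% CI on observed 3-month FWS with the observed n. Keep the zero-imputed mean beside it as a labelled worst-case row.
- **GAIS breakdown:** show the denominator in each stratum and the number of subjects without a 3-month GAIS.
- **Optional:** a repeated-measures model. SAP 8.1 expects the 510(k) submission to rest on 3-month results, so for that analysis the model should use only visits through 3 months.

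The cost is a change of wording and one table row, with no new data. The downside is that the observed-case mean assumes loss unrelated to outcome; the retained worst-case row lets the reader see how much that matters.

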### 7.5 Additional Endpoints

Other endpoints to be evaluated include:

1. FWS  $\geq 1$ -score improvement and  $\geq 75\%$  agreement with at least an “improved” rating by the subject on the modified GAIS. The modified GAIS is a measure of aesthetic improvement relative to the baseline, pre-treatment condition.
2. Magnitude of improvement measured by the mean change in FWS from baseline to 3 months visit.
3. Subject satisfaction with procedure recorded at the 3-month visit.
4. Achievement of re-epithelialization by facial zone and across all facial zones at the 10 day, 1-month and 3-month follow-up visits as reported by the investigator.
5. Mean duration until study subject feels comfortable going in public after treatment as reported by the study subject.
6. Daily 10-point Visual Analog Scale (VAS) pain assessment following treatment through the 10 day follow-up visit by diary day with a change from the VAS pain score at baseline.

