**Table 1. Study Required Procedures**

	Baseline/ Pre- Procedure Screening 	Procedure	10 Days	1 mo	3 mo	6 mo
			10+4/-1 days	30±7 days	90±10 days	180±14 days
Informed Consent	✓					
Assess Inclusion/Exclusion Criteria	✓					
Urine Pregnancy Test 	✓	✓				
Medical History	✓					
General Physical Exam	✓					
Review Medications	✓		✓	✓	✓	✓
Photographic Images 	✓		✓	✓	✓	✓
Fitzpatrick Skin Scale (FSS)	✓					
Fitzpatrick Wrinkle and Elastosis Scale (FWS) 	✓		✓	✓	✓	✓
Visual Analog Scale (10-point VAS) 		✓	✓	✓	✓	✓
Study Procedure		✓				
Subject Diary (10-point VAS) 		✓	✓			
Adverse Event Assessment		✓	✓	✓	✓	✓
Re-epithelialization and Down Time 			✓	✓	✓	
Modified Global Aesthetic Improvement Scale (GAIS) 			✓	✓	✓	✓

 Pre-procedure Screening assessments to take place within 21 days prior to undergoing the procedure.  
 Up to two urine pregnancy tests must be obtained prior to study procedure for females with child-bearing potential (one at pre-procedure screening and one on the day of the procedure prior to the procedure if screening and procedure are not performed on the same day).  
 Digital photographs of the subject's face will be taken and labeled according to Photography Instructions.  
 To be completed by Investigator and Independent Photographic Reviewers (IPRs).  
 To be completed by the study subject on a day of the procedure (prior to the procedure and immediately following the procedure) and at all follow-up visits.  
 To be completed by the study subject daily starting from the day of procedure (after procedure, at home) until the 10 day follow-up visit.  
 To be completed by Investigator and/or Independent Photographic Reviewer (as applicable) to capture achievement of epidermal recovery status at follow-up visits; and date when study subject felt comfortable, willing and able to go in public following study procedure (assessed at the 10 day follow-up visit).  
 To be completed by Investigator and study subject at all study follow-up visits.

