#### 8.4 Sample Size Considerations

The objective of this study is to demonstrate that study participants positively respond to the J-Plasma® therapy, thus the primary endpoint will be assessed via the percentage of study participants that demonstrated an improvement in the FWS from baseline to the 3-month visit. An improvement is clinically important when there is  $\geq 1$ -score change. The planned sample size to provide sufficient power for a statistical comparison of the proportion of treatment responders (P) versus a reasonable cutoff ( $P_0$ ) was based on a power calculation utilizing the (one proportion) binomial exact test based on the following assumptions.

- $H_0: P \leq P_0$  versus  $H_a: P > P_0$
- Type I error rate:  $\alpha = 0.05$  (one-sided)
- Population proportion under the null hypothesis:  $P_0 = 0.75$
- Population proportion under the alternative hypothesis:  $P = 0.90$
- Total N: 50 study participants

Based on the above assumptions, the study power is estimated to be approximately 88%. To account for possible missing data (up to 10% attrition), a total of 55 subjects will be enrolled. Other tests (i.e., a test of the mean improvement of FWS) would be expected to provide more power.

One study investigating the effects of radiofrequency energy on the improvement of appearance of wrinkles and rhytides (De Novo, Newa™) utilized a FWS cutoff as 75%, supporting this value in the present sample size computation.

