## 10 STATISTICAL ANALYSES

### 10.1 General Considerations

Data will be presented using summary statistics. For example, categorical data may be presented as proportions and counts; continuous data may be presented with the mean, median, minimum, maximum, and/or standard deviation.

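### If re-epithelialization is recorded as achieved or not, the mean and CI of the mean planned in SAP 10.9.1.3 break down when nearly all subjects have healed

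*SAP*

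**What the plan says.** SAP 7.5, item 4, lists the endpoint as "Achievement of re-epithelialization by facial zone and across all facial zones at the 10 day, 1-month and 3-month follow-up visits as reported by the investigator". Table 1, footnote 7, says that the assessment is made "to capture achievement of epidermal recovery status at follow-up visits". Neither place gives a score, a percentage healed or a unit.

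For the analysis, SAP 10.9.1.3 lists the number of observations, the mean with its 95% CI, the SD, the range and the median, and says that these statistics "will be used for summarizing the achievement of re-epithelialization by facial zone and across facial zones at all follow-up visits through the 3-month visit". Counts and percentages are not in that list.

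SAP 10.1 separates the two kinds of data: "categorical data may be presented as proportions and counts; continuous data may be presented with the mean, median, minimum, maximum, and/or standard deviation". The other responder-type outcomes follow that pairing. FWS response (10.5), GAIS improvement (10.6, 10.9.1) and adverse event rates (10.7) all get counts and percentages. The list in 10.9.1.3 is the one used for FWS change (10.9.1.1), days until comfortable in public (10.9.1.4) and the daily pain score (10.9.1.5).

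The source of the assessment also varies. Section 7.5 takes it "follow-up visits as reported by the investigator" alone. Section 10.9.1.3 and footnote 7 allow the investigator, the Independent Photographic Reviewers, or both.

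**The concern.** An achieved status at a visit reads as a categorical variable, yet the planned summary is the one for continuous data. For a 0/1 variable the mean is the proportion, so the point estimate survives. The SD, range and median add almost nothing. The interval is the real problem: a CI of the mean takes its width from the observed SD, and that SD shrinks to zero as the proportion approaches 100%.

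The result could be a table showing complete healing with no uncertainty, or an upper limit that is impossible for a proportion. SAP 8.1 expects the 510(k) submission to use the 3-month results, and 3 months is one of the visits at which this endpoint is summarised.

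The source wording raises a second, smaller question. No rule says whose reading is tabulated when both rater types have assessed a zone, so one summary could contain both.

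**Working it through.** **Inputs.** SAP 8.4 gives "Total N: 50 study participants" as the number for the power calculation and 55 as the number enrolled, so n=50 and n=55 are both used. The SAP states no figure for re-epithelialization that could be reproduced. Its one power figure, about 88% for the primary test, does reproduce: at N=50 the critical count is 43, exact alpha is 0.0453 and power is 0.878. It has no bearing on this point.

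**Assumptions.** (a) The item is recorded as achieved or not achieved. (b) Healing rates are unknown, so a range is shown.

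**Planned interval on 0/1 data.** With x healed of n and p = x/n:

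- SD = √[n p(1−p)/(n−1)]
- 95% CI of the mean = p ± t(0.975, n−1) × SD/√n

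Example, 54/55: p = 0.9818; SD = √(55 × 0.9818 × 0.0182/54) = 0.1348; SE = 0.1348/√55 = 0.0182; t = 2.005; half-width = 0.0364. The interval is 0.9454 to 1.0183.

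**Comparison with the exact (Clopper-Pearson) interval.** When all subjects have healed, the exact lower limit is 0.025^(1/n): 0.9351 for n=55 and 0.9289 for n=50.

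| Healed | CI of the mean | Exact 95% CI |
|---|---|---|
| 55/55 | 100% to 100% | 93.5% to 100% |
| 54/55 | 94.5% to 101.8% | 90.3% to 99.95% |
| 53/55 | 91.3% to 101.5% | 87.5% to 99.6% |
| 52/55 | 88.3% to 100.7% | 84.9% to 98.9% |
| 51/55 | 85.6% to 99.8% | 82.4% to 98.0% |
| 50/50 | 100% to 100% | 92.9% to 100% |
| 49/50 | 94.0% to 102.0% | 89.4% to 99.95% |
| 47/50 | 87.2% to 100.8% | 83.5% to 98.8% |
| 46/50 | 84.2% to 99.8% | 80.8% to 97.8% |

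At either n the upper limit passes 100% with one to three unhealed subjects. With four it is back in range.

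**Coverage at n=55.** Coverage is the sum of the binomial probabilities of every x whose interval contains the true rate.

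| True rate | Coverage of the nominal 95% CI of the mean |
|---|---|
| 80% | 93.4% |
| 85% | 91.7% |
| 90% | 91.5% |
| 95% | 93.9% |
| 97% | 81% |
| 98% | 67% |
| 99% | 42% |

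The fall at the end comes from the zero-width case. The chance that all 55 have healed is 0.97^55 = 0.187, 0.98^55 = 0.329 and 0.99^55 = 0.575, and each time the interval of 100% to 100% misses the true rate. That alone caps coverage at 81%, 67% and 42%. The exact interval covers at least 97% at these three rates. At a true rate of 97%, the chance of a zero-width or above-100% interval is about 92%.

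**Denominators by zone.** SAP 8.1 says that only applicable facial zones are treated, so a zone may have fewer than 50 subjects. The SAP gives no zone counts, so no figure is computed for them.

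**The case against.** The strongest objection is that the SAP never says the item is yes/no. It is to be read with the protocol and eCRFs (SAP section 2), which are not at hand. If the form records a percentage healed, or if the summary across zones is a share of healed zones, a mean and SD are usable. This stands, and it is why the point is conditional. It does not remove the need for an edit, because the SAP would then have to define that measure and the rule for combining zones.

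A reader might infer that the planned error bars are wrong at every visit. The documents do not support that. No healing rate is given, and at n=55 the interval loses only a few points of coverage at the rates from 80% to 95% shown above. The 10-day visit may well fall outside the range where it fails. The serious failure needs near-complete healing, which is an assumption here.

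A reader might also infer that a trial conclusion is at risk. It is not. This is one of the additional endpoints, with no hypothesis, test or success criterion. The number of observations and the mean are both reported, so the count can be recovered from the table. Section 10.1 leaves proportions and counts open for categorical data, but its wording is permissive and does not override the specific list in 10.9.1.3.

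On the source, it is tempting to say that 7.5 is right and the investigator must be the only rater. The SAP does not settle that: 10.9.1.3 and footnote 7 agree with each other, and 7.5 is the narrower text. Nor does any passage direct that the two kinds of reading be pooled. What stands is that the sections differ and no rule separates the raters.

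**Conclusion.** The point holds in a conditional and limited form. Section 10.9.1.3 applies continuous-data statistics to an endpoint that the SAP describes as an achieved status, and this departs from the SAP's own practice for its other responder outcomes.

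On an achieved/not-achieved scale, the planned interval has no width with no unhealed subjects and exceeds 100% with one to three. Its coverage is poor only at the top of the assumed range: at n=55, 81% or less for true rates of 97%, 98% and 99%.

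The conclusion rests on the inferred binary scale, on healing being nearly complete, and on denominators of 50 to 55. The harm is confined to the reported precision of a descriptive endpoint, some uninformative statistics and an unclear data source. The primary analysis and its power are not touched. The correction is worth making because it is cheap and the 3-month results are meant for a regulatory submission.

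**What to change.** In SAP 10.9.1.3, replace the list of statistics with counts and percentages and a binomial 95% CI. Report them at 10 days, 1 month and 3 months, for each treated facial zone (denominator: subjects treated and assessed in that zone) and for subjects with all treated zones healed. Either an exact (Clopper-Pearson) or a Wilson interval will do: the exact one guarantees at least nominal coverage, and the Wilson one is usually shorter. If the eCRF records something other than achieved or not achieved, state that measure in 7.5 and 10.9.1.3 and keep the mean for it.

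Reconcile the source of the assessment between 7.5 and 10.9.1.3 with footnote 7, and tabulate investigator and photographic-reviewer readings separately.

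The cost is SAP wording and table shells, with no new data or subjects. The intervals become slightly wider: at 54/55 the width goes from 7.3 points (101.8 − 94.5) to about 9.7 (99.95 − 90.3).

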## 8 STUDY DESIGN

### 8.1 Overview

This is a multi-center, single arm, evaluator-blind prospective study of 55 study subjects who are seeking a procedure to reduce the appearance of wrinkles and rhytides at up to 5 investigational centers in the United States.

Study subjects that meet study eligibility criteria and have provided informed consent will be enrolled in the study. During the procedure, the investigators will use J-Plasma® on applicable facial zones to reduce wrinkles and rhytides.

Study subjects will be followed immediately following the procedure, at 10 days, 1, 3, and 6 months post-procedure for study assessments.

Study enrollment is expected to occur over 3-6 months. Imaging and study assessments will continue through 6 months post-procedure. Total study duration is expected to be approximately 9-12 months. It is expected that the 510(k) application for the device will be submitted based on 3 month post-procedure results. However, this clinical trial will continue until every enrolled subject has reached 6 months following their procedure. At that time, the trial will be considered complete, the final results will be determined, and a final report will be prepared.

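### SAP 10.9.1.3 summarises a yes/no healing outcome with a mean and its confidence interval, and does not say whether the across-zones row counts zones or subjects

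*SAP*

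**What the plan says.** SAP 7.5 lists as its fourth additional endpoint "Achievement of re-epithelialization by facial zone and across all facial zones at the 10 day, 1-month and 3-month follow-up visits". SAP 10.9.1.3 gives the analysis: "Descriptive summary statistics (number of observations, mean, standard deviation, minimum, maximum, median, 95% confidence interval of the mean) will be used for summarizing the achievement". The same sentence covers both levels at once, "summarizing the achievement of re-epithelialization by facial zone and across facial zones at all follow-up visits through the 3-month visit", so it applies this one list both within each zone and to the across-zones result.

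Three things are left open:

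- **Unit.** Neither section says whether an observation in the across-zones row is a zone or a subject.
- **Combining rule.** Neither section says how several zones of one subject become one result. SAP 8.1 states that "the investigators will use J-Plasma® on applicable facial zones to reduce wrinkles and rhytides", so the number of treated zones may differ between subjects.
- **Counts.** The responder results in 10.5, 10.6 and 10.9.1 are to be given as counts and percentages. This one is not, and no count of subjects with every treated zone healed is planned.

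The rater also differs. SAP 7.5 names the investigator, whereas 10.9.1.3 has the result "as reported by the study investigator and/or Independent" Photographic Reviewers.

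**The concern.** The by-zone table needs one record per subject and zone. A programmer who produces the across-zones row by dropping the zone stratifier from those records complies with the text. One face then supplies several observations. These share the operator, the skin and the healing process, and an ordinary CI of the mean ignores that. If records from more than one rater were kept, there would be more rows per face still.

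Two things are at stake. The first is precision: the interval would look tighter than the number of subjects supports. The second is meaning: a share of healed zones is not a share of healed people, and the second is the figure a reader of a resurfacing study would look for. Another programmer, reading the same text as one result per subject, would report a different number. SAP 8.1 expects a 510(k) submission on the 3-month results, and 3 months is one of the visits concerned.

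**Working it through.** **The plan's own figures.** The SAP states no number for re-epithelialization. Its only calculation is the power in 8.4 ("Total N: 50 study participants", null 0.75, alternative 0.90, one-sided 0.05). That reproduces: the critical value is 43 responders, exact alpha 0.0453, power 0.878 against about 88% stated. It has no bearing on this endpoint.

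**Assumed inputs, none from the SAP.** Treated zones per subject k = 3 to 5; within-face correlation rho = 0.3 to 0.7; share of zones healed p = 0.85 or 0.90. The subject numbers, 50 evaluable and 55 enrolled, are from 8.4.

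**Step 1. Width of the CI if zones are pooled as rows.** Design effect DE = 1 + (k − 1) × rho. The correct interval is √DE times as wide as the naive one, and the naive nominal 95% CI covers about 2Φ(1.96/√DE) − 1.

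| k | rho | DE | √DE | Coverage |
|---|---|---|---|---|
| 3 | 0.3 | 1.6 | 1.26 | 87.9% |
| 3 | 0.5 | 2.0 | 1.41 | 83.4% |
| 3 | 0.7 | 2.4 | 1.55 | 79.4% |
| 5 | 0.3 | 2.2 | 1.48 | 81.4% |
| 5 | 0.5 | 3.0 | 1.73 | 74.2% |
| 5 | 0.7 | 3.8 | 1.95 | 68.5% |

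A beta-binomial simulation (20,000 runs, 55 subjects, p = 0.85) agrees at the two extremes: 86.3% and 69.4%. With a weak correlation of 0.1 the effect is small: √DE is 1.10 for 3 zones and 1.18 for 5.

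**Step 2. Share of zones against share of subjects.** Under a beta-binomial with rho = 0.5 the two parameters are p and 1 − p. With p = 0.85:

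- 3 zones: P(all healed) = (0.85 × 1.85 × 2.85)/(1 × 2 × 3) = 0.747.
- 5 zones: 0.747 × (3.85 × 4.85)/(4 × 5) = 0.697.

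So a pooled 85% goes with about 75% or 70% of subjects fully healed, a gap of 10 to 15 percentage points.

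The answer depends on rho. With p = 0.90, the share of subjects with at least one unhealed zone is:

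- 3 zones: from 1 − 0.90 = 10% (rho = 1) to 1 − 0.90³ = 27% (rho = 0).
- 5 zones: from 10% to 1 − 0.90⁵ = 41%.

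That is 5 to about 20 of 50 subjects behind the same pooled 90%.

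**Step 3. What the by-zone rows add.** The number of subjects with any unhealed zone is at least the largest single-zone count of failures and at most their sum. If 50 subjects have three treated zones each and every zone is 90% healed (5 failures per zone), the number is between 5 and 3 × 5 = 15. The by-zone rows bound the figure without giving it.

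**Step 4. One value per subject.** Clustering is then gone, but the statistic still fits poorly near 100%.

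- 49 of 50 healed: mean 0.98, SD = √(50/49 × 0.98 × 0.02) = 0.1414, SE = 0.1414/√50 = 0.0200, t(49) = 2.010. The interval is 0.98 ± 0.040, or 94.0% to 102.0%. The exact binomial interval is 89.4% to 99.9%.
- 50 of 50 healed: SD = 0, so the interval is 100% to 100%. The exact lower limit is 0.025^(1/50) = 92.9%.

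**The case against.** A reader might infer that the SAP treats facial zones as independent. It does not say so. The list of statistics is stock text: it recurs for the change in FWS (10.9.1.1) and for the time until the subject is comfortable in public (10.9.1.4), where the unit is naturally the subject. The reference to number of observations therefore does not settle the unit here. The wording in 7.5, across all facial zones, can equally mean one result per subject, healed everywhere or not. On that reading there is no clustering and no unequal weighting. This part of the objection stands, and Steps 1 and 2 therefore apply only if zones are pooled.

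A reader might also infer that the plan hides subjects with an unhealed zone. That goes too far. The by-zone results at three visits show unhealed zones and limit how many subjects can be affected (Step 3).

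The definition of zones, the recording of which were treated and the form of the healing item may sit in the protocol or eCRFs, which the SAP says to read alongside it. Their absence from the SAP is not counted against it. If the eCRF records a graded percentage of healing, a mean would be defensible, although the endpoint's wording suggests yes/no.

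Finally, every input to Steps 1 and 2 is assumed, and one healing rate cannot represent visits from 10 days to 3 months. When nearly all zones are healed the gap shrinks: with 98% healed, at least 1 − 3 × 0.02 = 94% of subjects (3 zones) or 1 − 5 × 0.02 = 90% (5 zones) are fully healed, whatever the correlation.

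None of this supplies the missing unit, or makes a CI of the mean suitable for a yes/no result near 100%.

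**Conclusion.** The point holds as a specification gap with a poorly matched statistic, at low severity. SAP 10.9.1.3 fixes the statistics but not the unit or the rule for combining zones, and both readings comply with it.

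If zones are pooled, the interval should be about 1.26 to 1.95 times as wide (3 to 5 zones, correlation 0.3 to 0.7, equal numbers of zones per subject), and the rate does not show how many subjects are fully healed. If subjects are counted, these problems vanish, but the CI of the mean exceeds 100% at 49 of 50 and collapses at 50 of 50. That last result needs no assumption about zones or correlation, only a yes/no outcome.

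The documents do not support the claim that the sponsor has chosen an analysis assuming independence. The endpoint is one of six additional ones and is descriptive, with no test or threshold. The primary efficacy analysis and the sample size are unaffected.

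**What to change.** In SAP 10.9.1.3:

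1. Define for each subject and visit a binary variable, all treated zones re-epithelialized (yes/no), and report it as n/N, percentage and exact binomial 95% CI at 10 days, 1 month and 3 months.
2. Report each zone as n/N and percentage, with subjects treated in that zone as the denominator.
3. If a pooled zone rate is kept, label it as a share of zones and use a subject-clustered CI (cluster-robust or GEE).
4. Remove the mean, SD and median for this yes/no endpoint.
5. State whose rating is analysed, so that 7.5 and 10.9.1.3 agree and each zone contributes one record per visit.

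The cost is a few lines of SAP text and one derived variable, with no new data if zone-level healing and treated zones are already recorded. The drawback for the sponsor is that the subject-level figure can be no higher than the lowest by-zone rate when all subjects have the same zones treated, so healing may look less favourable.
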